5.8.6 Disease Status Survey

For change in disease status of prospective survey data, number (%) of subjects with changes from baseline to each visit will be summarized by each category for overall subjects and a subgroup of subjects with corticosteroid use (Yes/No). If there are multiple symptoms under a category, the highest score/worse case of all available symptoms was selected for the category in the summary.

Data from the retrospective survey in studies 007 and 007e will be summarized separately.

5.8.7 Echocardiogram

The LVEF will be summarized by visit and change from baseline to each post baseline visit will be summarized descriptively for overall subjects. Similarly the LVEF will be summarized for each actual age.

5.9 Subgroup analysis

5.9.1 Six minute walk distance subgroups

The by-visit summary on the observed values and change from baseline to each post baseline visit values will be performed descriptively for each 6MWT subgroup (<300 meters, ≥300-<400 meters, ≥400 meters) on 6MWT, TFT, and NSAA endpoints.

5.9.2 Corticosteroids type subgroups

The by-visit summary on the observed values and change from baseline to each post baseline visit values will be performed descriptively for each corticosteroid type prior to study entry (deflazacort vs prednisone/prednisolone) on 6MWT and TFTs. The Kaplan-Meier method will be applied to the analysis of age at loss of ambulation and age at FVC <1 liter each subgroup.

5.9.3 Cumulative duration of corticosteroids use subgroups

The cumulative duration of corticosteroid use prior to study entry will be categorized as <12 months vs ≥12 months. The by-visit summary on the observed values and change from baseline to each post baseline visit values will be performed descriptively for each subgroup on 6MWT and TFTs. The Kaplan-Meier method will be applied to the analysis of age at loss of ambulation and age at FVC <1 liter for each subgroup.

5.9.4 Other subgroups

Corticosteroids use in the study will be reviewed. If any other corticosteroids subgroup is clinically meaningful, the subgroup analyses on it will be performed on all efficacy endpoints.

6 DATA HANDLING

6.1 Analysis Visits based on Visit Windows

Since some subjects had early terminations or unscheduled visits in during, the derived analysis visits will be generated by visit window defined as follows.

The derived visits will be generated by visit window defined as follows.

Let ADY=assessment date –first dose date +1.

```
IF .<= ADY <=1 THEN AVISIT= BASELINE AND AVISITN=1;
IF 42<= ADY <=126 THEN AVISIT=WEEK 12 AND AVISITN=2;
IF 126<ADY <=210 THEN AVISIT=WEEK 24 AND AVISITN=3;
IF 210<ADY <=294 THEN AVISIT=WEEK 36 AND AVISITN=4;
IF 294<ADY <=378 THEN AVISIT=WEEK 48 AND AVISITN=5;
IF 378<ADY <=462 THEN AVISIT=WEEK 60 AND AVISITN=6;
IF 462<ADY <=546 THEN AVISIT=WEEK 72 AND AVISITN=7;
IF 546<ADY <=630 THEN AVISIT=WEEK 84 AND AVISITN=8;
IF 630<ADY <=714 THEN AVISIT=WEEK 96 AND AVISITN=9;
IF 714<ADY <=798 THEN AVISIT=WEEK 108 AND AVISITN=10;
IF 798<ADY <=882 THEN AVISIT=WEEK 120 AND AVISITN=11;
IF 882<ADY <=966 THEN AVISIT=WEEK 132 AND AVISITN=12;
IF 966<ADY <=1050 THEN AVISIT=WEEK 144 AND AVISITN=13;
IF 1050<ADY <=1134 THEN AVISIT=WEEK 156 AND AVISITN=14;
IF 1134<ADY <=1218 THEN AVISIT=WEEK 168 AND AVISITN=15;
IF 1218<ADY <=1302 THEN AVISIT=WEEK 180 AND AVISITN=16;
IF 1302<ADY <=1386 THEN AVISIT=WEEK 192 AND AVISITN=17;
IF 1470<ADY <=1554 THEN AVISIT=WEEK 216 AND AVISITN=19;
IF 1554<ADY <=1638 THEN AVISIT=WEEK 228 AND AVISITN=20;
IF 1638<ADY <=1722 THEN AVISIT=WEEK 240 AND AVISITN=21
IF 1722<ADY <=1806 THEN AVISIT=WEEK 252 AND AVISITN=22
IF 1806<ADY <=1890 THEN AVISIT=WEEK 264 AND AVISITN=23
IF 1890<ADY <=1974 THEN AVISIT=WEEK 276 AND AVISITN=24
IF 1974<ADY <=2058 THEN AVISIT=WEEK 288 AND AVISITN=25
IF 2058<ADY <=2142 THEN AVISIT=WEEK 300 AND AVISITN=26
```

IF 2142<ADY <=2226 THEN AVISIT=WEEK 312 AND AVISITN=27

IF 2226<ADY <=2310 THEN AVISIT=WEEK 324 AND AVISITN=28

IF 2310<ADY <=2394 THEN AVISIT=WEEK 336 AND AVISITN=29.

If there are more than 1 valid assessment within one visit window, the last one will be chosen as the analysis value.

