1.2. Study Design

This study comprises a Phase 3, open-label study of ataluren in patients with nmDBMD who previously received ataluren at an investigator site in a prior PTC-sponsored clinical study. A separate open-label study (PTC124-GD-016-DMD) is being conducted for nmDBMD patients who previously received ataluren at an investigator site in the United States (US).

All participating sites must have had at least 1 patient that received at luren treatment in a prior PTC-sponsored clinical study in DBMD. It is planned that up to ~96 patients will be enrolled.

Subjects will receive ataluren 3 times per day (TID) at respective morning, midday, and evening doses of 10 mg/kg, 10 mg/kg, and 20 mg/kg, for approximately 240 weeks. Study assessments will be performed at clinic visits during screening, on the first day of ataluren dosing, and then every 12 weeks during the ataluren treatment period.

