7.2.15. Echocardiogram

An echocardiogram will be obtained at Screening (Visit 1), Week 60 (Visit 7), Week 108 (Visit 11), Week 156 (Visit 15) and Week 216 (Visit 20). In addition, an echocardiogram will be

obtained at the Post-Treatment Visit (6 weeks post discontinuation of ataluren) in patients who discontinue the study after 240 weeks of treatment.

7.2.16. 6-Minute Walk Test

6MWD will be assessed in those patients who are ambulatory (able to run/walk 10 meters in ≤30 seconds) at study entry, using standardized procedures [McDonald 2010] (see Study Manual). The 6MWT will be performed at Screening (Visit 1), Week 24 (Visit 4), Week 48 (Visit 6), Week 72 (Visit 8), Week 96 (Visit 10), Week 120 (Visit 12), Week 144 (Visit 14), Week 168 (Visit 16), Week 192 (Visit 18), Week 216 (Visit 20) and Week 240 (Visit 22 End-of-Treatment/Premature Discontinuation).

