7.2.17. Timed Function Tests

Timed function tests will performed in those patients who are ambulatory at study entry, and include the time taken to stand from supine and time taken to run/walk 10 meters [Mendell 1989, Griggs 1991, Beenakker 2005a, Pradhan 2006] (see Study Manual). These parameters will be monitored at Screening (Visit 1), Week 48 (Visit 6), Week 96 (Visit 10), Week 144 (Visit 14), Week 192 (Visit 18) and Week 240 (Visit 22 End-of-Treatment/Premature Discontinuation).

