5 STATISTICAL ANALYSIS

5.1 General Statistical Considerations

Summary tables for continuous variables will contain the following statistics: n, mean, standard deviation, standard error, 95% confidence intervals (CIs) on the mean, median, minimum, and maximum. Summary tables for categorical variables will include N, n, and percentages. In by-visit summaries, the analysis visits will be derived via visit mapping windows.

By-patient listings will be created for each CRF module. The data will be listed by center/subject ID and visit.

In addition, all analyses will be performed by corticosteroid use (yes or no before or during the study), by ambulatory status (ambulatory or non-ambulatory) at baseline, and overall, unless specified otherwise.

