5.8 Secondary Variables

Subject [REDACTED] will be excluded from the As-Treated population in the analyses of all secondary endpoints.

5.8.1 6-Minute Walk Test

The distance walked at each visit and the change from baseline at each post baseline visit, as obtained from the 6-minute walk test (6MWT), will be summarized descriptively for ambulatory subjects with non-missing baseline 6MWT assessments. The distance walked at each will also be summarized for each actual age.

The endpoint will also be analyzed by means of a mixed model repeated measures (MMRM). An unstructured variance-covariance will be assumed and the estimation method will be the default, ReML. The model will include the factors for treatment, visit, age (6-11, 12-17, and ≥ 18 years), use of corticosteroids at baseline (yes vs no), and baseline 6MWD category (< 300 meters, ≥ 300 - < 400 meters, ≥ 400 meters), and baseline 6MWD as a covariate. Visit is considered as a categorical variable. From this analysis the mean change at each visit will be evaluated. If the model cannot converge, compound symmetry variance-covariance structure will be assumed.

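### One 12-weekly visit grid is applied to tests scheduled every 24 or 48 weeks, so many leaving-visit results miss the scheduled rows and add sparse visit levels to the MMRM.

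*SAP*

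**What the plan says.** SAP 5.1 sets the scope: "In by-visit summaries, the analysis visits will be derived via visit mapping windows". SAP 6.1 gives the reason, "Since some subjects had early terminations or unscheduled visits in during, the derived analysis visits will be generated by visit window defined as follows", and then one list of windows, beginning "IF 42<= ADY <=126 THEN AVISIT=WEEK 12 AND AVISITN=2" and continuing in 84-day steps to Week 336. No assessment has windows of its own. For several results in one window the rule is: "If there are more than 1 valid assessment within one visit window, the last one will be chosen as the analysis value".

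That grid matches the clinic visits, which take place on the first dosing day and "then every 12 weeks during the ataluren treatment period". It does not match the functional tests:

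- **Timed function tests** (Protocol 7.2.17): "These parameters will be monitored at Screening (Visit 1), Week 48 (Visit 6), Week 96 (Visit 10), Week 144 (Visit 14"), and so on to Week 240. NSAA (7.2.18) and EK (7.2.19) follow the same 48-week schedule.
- **6MWT** (Protocol 7.2.16): "The 6MWT will be performed at Screening (Visit 1), Week 24 (Visit 4), Week 48 (Visit 6), Week 72 (Visit 8"), and so on. Spirometry (7.2.20) has the same 24-week schedule.

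Protocol 7.2.1.3 requires the Week 240 procedures at a Premature Discontinuation Visit if the last site visit was more than 3 weeks earlier. Boys moving to commercial drug have an End-of-Treatment Visit whenever they switch.

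For the 6MWT, SAP 5.8.1 specifies an MMRM with unstructured covariance and adds: "Visit is considered as a categorical variable". If the model does not converge, compound symmetry is used. SAP 5.8.2 applies the same model to the timed function tests.

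**The concern.** A boy who leaves near Week 72 has a timed function test that the grid labels Week 72. No timed function test is scheduled then, and no rule moves the result to a scheduled visit. The grid was introduced to place such results, yet for the 24- and 48-weekly tests it often puts them in rows that hold only a few leavers and unscheduled tests. Where a leaving result does fall in a scheduled window but after an on-time test, the last-value rule makes it replace the on-time value.

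Two things are at stake. The descriptive change-from-baseline tables, including the by-visit subgroup tables of SAP 5.9, lose many final results from their scheduled rows. And if the MMRM uses the derived visits, the only analysis visits the SAP defines, each off-schedule week becomes another visit level with few records. The paired t-tests were removed (SAP 7), so this MMRM is the only model of change for the 6MWT and timed function tests. A labelling rule could therefore decide its covariance structure.

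This need not be rare. SAP 5.2 says the sponsor has decided to discontinue the study and lists transition to commercial drug as another exit. Either can produce final tests at arbitrary weeks.

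**Working it through.** The documents give no figure for misplaced results, so there is none to reproduce.

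**Inputs.** Windows: SAP 6.1, target day = 7 × week, ±42 days. Schedules: Protocol 7.2.16 to 7.2.20. The 3-week condition: Protocol 7.2.1.3. Leaving times: not given; uniform over days 2 to 1679 is assumed, then varied.

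**Window count.** Weeks 12 to 228 in steps of 12 give 19 nominal weeks. Of these, 4 are multiples of 48 and 9 are multiples of 24.

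- 48-weekly tests: (19 − 4)/19 = 15/19 = 79% off schedule.
- 24-weekly tests: (19 − 9)/19 = 10/19 = 53% off schedule.

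**Day-by-day mapping.** Of leaving days 2 to 1679, 1,240 are more than 21 days after the preceding 12-weekly visit.

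| Where the leaving result falls | 24-weekly | 48-weekly |
|---|---|---|
| Window with no scheduled test | 559 (45.1%) | 869 (70.1%) |
| No window (days before 42; Week 204) | 82 (6.6%) | 82 (6.6%) |
| Scheduled window, before target | 410 (33.1%) | 205 (16.5%) |
| Scheduled window, on or after target | 189 (15.2%) | 84 (6.8%) |

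The first two rows miss the scheduled means: 45.1 + 6.6 = 51.7% and 70.1 + 6.6 = 76.7%. The last row replaces an on-time value. The text shows no Week 204 line (AVISITN goes from 17 to 19), which may be a loss in reading the file. If the line exists, 62 of the 82 days move from the second row to the first and the totals do not change.

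**Range.** With uniform leaving, exponential leaving (10% to 70% gone by Week 240) or late-weighted leaving, with and without the 3-week condition, the share missing the scheduled means is 49% to 54% (24-weekly) and 74% to 79% (48-weekly).

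**Covariance parameters**, k(k+1)/2 for k visit levels:

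- 5 scheduled timed-function visits: 5 × 6/2 = 15.
- 10 scheduled 6MWT visits: 10 × 11/2 = 55.
- 19 printed post-baseline levels to Week 240: 19 × 20/2 = 190.
- 27 printed levels to Week 336: 27 × 28/2 = 378, the ceiling.

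At most about 96 boys enrol, and only ambulatory boys with a baseline value enter these models. A boy normally has one leaving visit, so two different off-schedule leaving weeks are seldom or never observed in the same boy. Little or nothing in the data then informs their covariance.

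**After the change** (windows of ±84 and ±168 days, closest to target, on-time tests assumed present, same 1,240 days):

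| | 24-weekly | 48-weekly |
|---|---|---|
| Supplies the next scheduled visit | 620 (50%) | 620 (50%) |
| Loses to an on-time value in the same window | 558 (45%) | 496 (40%) |
| Before the first window opens | 62 (5%) | 124 (10%) |

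Opening the first window at day 2 brings in the last row, so 50 + 5 = 55% and 50 + 10 = 60% supply the next scheduled visit, against 33.1% and 16.5% under the printed grid.

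**The case against.** The strongest reply is that little is lost. Off-schedule 6MWT and timed-function values stay in the MMRM likelihood and inform scheduled-visit means through within-patient correlation. Summaries by actual age, the Kaplan-Meier analyses of loss of ambulation and FVC below 1 liter, and the natural-history comparisons do not use the grid. NSAA, EK and spirometry have no MMRM in SAP 5.8. The study is open-label and single-arm, safety is primary, and there is no formal hypothesis. All of this stands, and it confines the point to the descriptive by-visit tables and the MMRM covariance.

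A reader might infer that by-visit decline is understated because worsening boys leave. The documents do not show this. Protocol 6.2.1 and SAP 5.2 list commercial availability, marketing authorization, transfer to another study and sponsor termination among the exits, and none implies worsening. Nor do scheduled rows hold only boys who stayed: they contain leavers' earlier on-time results and some leaving results.

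A reader might also infer that the MMRM cannot be fitted at all. The SAP has a fallback, and 378 would need records in every printed level, although visits beyond Week 240 exist only under Version 6.1 for Canadian sites.

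The remedy has its own loss. Week 72 is day 504, the last day of a ±168-day Week 48 window, so that result yields to an on-time Week 48 value and does not reach Week 96. Restricting the MMRM to scheduled levels also takes such results out of the likelihood. In a progressive disease, reporting an early result under a later visit can itself make decline look smaller. These costs are real and must be stated.

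**Conclusion.** The point holds in limited form. With uniform leaving times, about three quarters of leavers' final timed-function, NSAA and EK results (77%; 74% to 79% across scenarios) and about half of their 6MWT and spirometry results (52%; 49% to 54%) miss the scheduled rows of the descriptive tables. About 7% and 15% respectively would replace an on-time value. It would be wrong to say that most results are affected for every test, or that they disappear from the analysis.

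In the 6MWT and timed-function MMRM, sparse off-schedule levels make the unstructured covariance hard or impossible to fit. The compound-symmetry fallback, with equal correlation between visits 12 weeks apart and years apart, could then be adopted because of how visits were labelled. This assumes that the MMRM uses the derived visits. The direction of any bias in by-visit decline is uncertain. All shares rest on assumed leaving times, and the number of leavers is not given. The outcomes are secondary, so this is an inexpensive improvement and does not threaten the primary safety analysis.

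**What to change.** In SAP 6.1, keep the printed grid for 12-weekly assessments and add windows by test schedule:

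- **Timed function tests, NSAA, EK:** Week 48 = days 2 to 504; Week 96 = 504<ADY<=840; Week 144 = 840<ADY<=1176; Week 192 = 1176<ADY<=1512; Week 240 = 1512<ADY<=1848.
- **6MWT, spirometry:** Week 24 = days 2 to 252, then each 24-week target ±84 days.
- Continue both to Week 336 for Version 6.1, assuming the same test intervals apply there.
- For these tests, use the valid result closest to target, with a stated tie rule, in place of the last one.
- Use only scheduled visit levels in the MMRM.
- Keep the current 12-week grid as a sensitivity table.

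The cost is SAP wording and programming; no new data are needed. The SAP should state the drawbacks. A result up to 24 weeks off target (12 weeks for the 24-weekly tests) is reported under the nearest visit. In the first window, opened at day 2, a result can be almost 48 (or 24) weeks early. A leaving result taken after an on-time test in the same window, about 40% (48-weekly) to 45% (24-weekly) of leaving results under uniform leaving, then appears only in listings, by-age summaries and, where the test feeds one, the Kaplan-Meier analyses.

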7.2.1.2. Treatment Visits during Study

Each subject will subsequently return to the clinical research facility during Week 12 (Visit 3), Week 24 (Visit 4), Week 36 (Visit 5), Week 48 (Visit 6), Week 60 (Visit 7), Week 72 (Visit 8), Week 84 (Visit 9), Week 96 (Visit 10), Week 108 (Visit 11), Week 120 (Visit 12), Week 132 (Visit 13), Week 144 (Visit 14), Week 156 (Visit 15), Week 168 (Visit 16), Week 180 (Visit 17), Week 192 (Visit 18), Week 204 (Visit 19), Week 216 (Visit 20), Week 228 (Visit 21) and Week 240 (Visit 22).

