7.2.1.4 Post-Treatment Visits

All patients who discontinue at luren must return for a Post-Treatment Visit at the investigator site 6 weeks (±7 days) after the last dose of at luren for final study-related evaluations. If the End-of-Treatment Visit occurs >6 weeks after the last dose of at luren, the Post-Treatment Visit does not need to be performed. For patients discontinuing the study to transition to commercially available at luren, an End-of-Treatment visit should be performed for that patient. However, a 6-Week Post-Treatment Visit is not required for these patients.

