7.2.11. Serum Biochemistry Laboratory Assessment

Biochemistry laboratory assessments will include sodium, potassium, chloride, bicarbonate, blood urea nitrogen, creatinine, magnesium, calcium, phosphorus, uric acid, glucose, total protein, albumin, globulin, albumin:globulin ratio, bilirubin (direct and indirect), AST, ALT, GGT, CK, lactate dehydrogenase (LDH), alkaline phosphatase, total cholesterol, high-density lipoprotein (HDL), low-density lipoprotein (LDL), triglycerides, and cystatin C. These parameters will be measured at Screening (Visit 1), Week 1 (Visit 2), Week 12 (Visit 3), Week 24 (Visit 4), Week 36 (Visit 5), Week 48 (Visit 6), Week 60 (Visit 7), Week 72 (Visit 8), Week 84 (Visit 9), Week 96 (Visit 10), Week 108 (Visit 11), Week 120 (Visit 12), Week 132

(Visit 13), Week 144 (Visit 14), Week 156 (Visit 15), Week 168 (Visit 16), Week 180 (Visit 17), Week 192 (Visit 18), Week 204 (Visit 19), Week 216 (Visit 20), Week 228 (Visit 21), Week 240 (Visit 22 End-of-Treatment/Premature Discontinuation) and at the Post-Treatment Visit (6 weeks post discontinuation of ataluren). Subjects should have fasted for at least 8 hours prior to blood collection. Biochemistry parameters will be analyzed by the central laboratory. The Covance Central Laboratory Manual should be consulted for collection, processing, and shipping details.

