1 OVERVIEW

This statistical analysis plan (SAP) details the statistical methods to be used in the analyses and presentation of the data collected in Study PTC124-GD-019-DMD, also referred to as Study 019. Preparation of this SAP incorporates statistical design elements present in the protocol Version 5.0 (dated 18 November 2015). Details are documented in Sections 1-7.

In addition to the protocol defined analyses, a natural history control using the Cooperative International Neuromuscular Research Group (CINRG) will be utilized in order to help to better understand the long-term ataluren data. The planned analysis will be presented in Section 8.

After the implement of protocol Version 5.0, the sponsor has developed the protocol Version 6.1 (dated 08 March 2017) specifically for Canadian sites only for ethics approval when they finished all visits per Version 5.0 and were waiting to roll into another open-label nmDMD Study PTC124-GD-016-DMD conducted in the United States (US). The maximal scheduled visit in Version 5.0 was extended from week 240 to week 336 in Version 6.1. All data collected based on both Versions will be summarized together.

Where conflicts exist between this SAP and the study protocols, the information contained in this SAP supersedes the protocol.

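### SAP 6.1 visit windows omit Week 204 and have no Post-Treatment visit, so by-visit safety tables lose a scheduled visit and file off-drug values under treatment weeks

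*SAP*

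**What the plan says.** SAP 5.1 sends all by-visit summaries through the mapping windows of SAP 6.1. Those windows use study day counted from first dose; neither last dose nor the nominal visit on the case report form enters.

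- Two consecutive lines of SAP 6.1 read "IF 1302<ADY <=1386 THEN AVISIT=WEEK 192 AND AVISITN=17" and "IF 1470<ADY <=1554 THEN AVISIT=WEEK 216 AND AVISITN=19". No line carries AVISITN 18.
- Protocol 7.2.1.2 schedules the visit in between: "Week 204 (Visit 19), Week 216 (Visit 20), Week 228 (Visit 21) and Week 240 (Visit 22".
- Ties are settled thus: "If there are more than 1 valid assessment within one visit window, the last one will be chosen as the analysis value". The SAP does not define a valid assessment.
- Protocol 7.2.1.4 says that patients who stop ataluren "must return for a Post-Treatment Visit at the investigator site 6 weeks (±7 days) after the last dose". Both schedule tables (Protocol Table 4, SAP Table 1) give this visit its own column.
- Biochemistry, for example, is due at Week 240 ("Visit 22 End-of-Treatment/Premature Discontinuation) and at the Post-Treatment Visit"), and Protocol 7.2.5, 7.2.9, 7.2.10, 7.2.12 and 7.2.13 say the same for vital signs, weight, hematology, ACTH/cortisol and urinalysis.
- An echocardiogram is "obtained at the Post-Treatment Visit (6 weeks post discontinuation of ataluren) in patients who discontinue the study after 240 weeks of treatment".
- SAP Section 1 states: "The maximal scheduled visit in Version 5.0 was extended from week 240 to week 336 in Version 6.1". Data from the two versions are pooled.

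SAP Section 7, which lists changes from the protocol, mentions neither the loss of Week 204 nor the handling of the Post-Treatment Visit.

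**The concern.** Safety, including laboratory abnormalities, is the primary endpoint. Its by-visit display consists of the laboratory summaries and shift tables (SAP 5.7.2) and the vital-sign and weight tables (SAP 5.7.3). Two things go wrong if the windows are programmed as printed.

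First, Week 204 values, and any discontinuation-visit values on days 1387 to 1470, disappear from these tables.

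Second, values taken about six weeks off drug are labelled as treatment weeks, whenever a patient stops. They either displace the last on-drug value or appear under the next treatment week. For patients completing under Version 5.0 that next label is Week 252, which is a genuine on-treatment visit under Version 6.1, so one row can mix on-drug and off-drug patients. A laboratory shift that reverses, or first appears, after stopping would be read at the wrong time and under the wrong exposure.

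**Working it through.** **Inputs**

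- Windows: SAP 6.1.
- Visit tolerance ±7 days: Protocol Table 4.
- Post-Treatment Visit at last dose + 42 ± 7 days, that is +35 to +49: Protocol 7.2.1.4.
- Study day = assessment date − first dose date + 1, so a week-*w* visit is day 7*w* or 7*w* + 1 depending on how weeks are counted. Both are shown.

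**1. Reproducing the printed grid.** The rule 7*w* − 42 < ADY ≤ 7*w* + 42, with AVISITN = *w*/12 + 1, gives all 27 printed post-baseline windows. The only difference is that Week 12 also takes day 42.

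- Week 192: 1344 − 42 = 1302; 1344 + 42 = 1386; AVISITN 192/12 + 1 = 17.
- Week 216: 1512 − 42 = 1470; 1512 + 42 = 1554; AVISITN 216/12 + 1 = 19.
- Week 204 by the same rule: 1428 − 42 = 1386; 1428 + 42 = 1470; AVISITN 18. This window is absent.

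**2. Week 204.**

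- Unmapped days: 1470 − 1386 = 84.
- Allowed visit days are 1421–1435 (centre 1428) or 1422–1436 (centre 1429). All 15 of 15 are unmapped either way.
- This is one of 240/12 = 20 scheduled 12-weekly visits.
- Seven assessment types lose the row: vital signs, weight, hematology, biochemistry, ACTH/cortisol, urinalysis and the disease status survey.
- The only other unmapped stretch up to day 2394 is days 2–41, where no 12-weekly visit falls.

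**3. Post-Treatment Visit, last dose on a scheduled visit day.** Each window ends 42 days after 84*k*, where *k* = *w*/12.

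- Last dose on day 84*k*: offsets 35 to 42 stay in the same window (8 of 15); 43 to 49 pass out of it (7 of 15).
- Last dose on day 84*k* + 1: offsets 35 to 41 stay (7 of 15); 42 to 49 pass out (8 of 15).

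This holds for a stop at any scheduled week from 12 to 240 except 204. After a Week 192 stop, the days that pass out fall in the gap. After a Week 204 stop, the 8 or 7 days that should be Week 204 fall in the gap and the rest become Week 216.

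Example: last dose on day 1680 (Week 240) puts the visit on days 1715–1729. Days 1715–1722 map to Week 240 and displace the on-drug value; days 1723–1729 map to Week 252. A Version 6.1 on-treatment Week 252 visit (day 1764 or 1765, ±7) also maps wholly to Week 252.

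**4. Week 240 completers, ±7 days on both visits.** Let *a* and *b* be the two deviations, each from −7 to 7, giving 15 × 15 = 225 timings.

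- Centre 1680: same window if *a* + *b* ≤ 0. Fifteen pairs sum to zero, so the count is (225 − 15)/2 + 15 = 120, and 120/225 = 53.3%.
- Centre 1681: same window if *a* + *b* ≤ −1. The count is (225 − 15)/2 = 105, and 105/225 = 46.7%.
- The remaining timings become Week 252.

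**5. Dropping the visit-day assumption.** Take every last-dose day from 84 to 1687 and every offset from +35 to +49, equally weighted: 1604 × 15 = 24,060 combinations. The Post-Treatment Visit falls in the window of the last dose in 11,376 (47.3%), in a later treatment-week window in 11,424 (47.5%), and in the Week 204 gap in 1,260 (5.2%).

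**6. LVEF.** Protocol 7.2.15 lists on-treatment echocardiograms at Weeks 60, 108, 156 and 216, and none at Week 240. On that list, the post-treatment echocardiogram of a 240-week completer appears as Week 240 or Week 252 without displacing anything. Protocol Table 4 is less clear, because 240 = 4 × 60 = 5 × 48 satisfies both of its periodic columns. If a Week 240 echocardiogram were taken, displacement could occur there too.

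**The case against.** **The Week 204 line may only be a typographical or text-conversion loss.** Numbering jumps from 17 to 19 in an otherwise regular list, so the intended window is obvious. This is fair. The line should be checked against the SAP PDF, and if it is there, that part falls away. If it is not, the SAP states that it supersedes the protocol, so the text should be corrected. The Post-Treatment point does not depend on this line.

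**Few patients may be affected.** Patients moving to commercial drug need no Post-Treatment Visit, nor do those whose End-of-Treatment Visit comes more than 6 weeks after last dose (Protocol 7.2.1.4). Patients rolling into Study 016 without stopping may have none either. This stands: the number is unknown and could be small.

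**The safety consequence is limited.** TEAE, SAE and exposure-adjusted tables do not use these windows, by-patient listings keep every value, and the by-visit tables are descriptive. This also stands. The Table 2 abnormality summary and the hypertension counts are not stated to be by visit. I read them as whole-study counts that still use these values, but that is an inference.

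**The SAP's own treatment-emergent period runs to 6 weeks after last dose.** That rule attributes adverse events; it does not make an off-drug laboratory value a Week 240 on-treatment value. Visits at +43 to +49 days fall outside even that period.

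**A valid assessment might be meant to exclude off-drug values.** Nothing in the SAP says so.

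**Conclusion.** The concern holds as the SAP is printed. Week 204 has no analysis window: 84 days, one of 20 scheduled 12-weekly visits and seven assessment types. Six assessment types from the Post-Treatment Visit are labelled as treatment weeks or fall in the gap. Where last dose is on a scheduled visit day (other than Week 204), 7 or 8 of the 15 allowed days put the off-drug value in the last on-drug window, where the last-value rule makes it the analysis value.

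The percentages are shares of allowed timings with equal weight, not estimates of patients affected. They assume last dose on the day of the last on-drug visit, except in step 5. The number of patients is unknown, at most about 96, and the direction of bias cannot be stated. I would not expect the adverse-event conclusions to change, but the by-visit rows for the primary safety endpoint would be wrong as labelled. This should be fixed before the tables are programmed. Confidence is high for the Post-Treatment part. The Week 204 part is conditional on the PDF check.

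**What to change.** 1. After checking the PDF, add the missing window to SAP 6.1: `1386 < ADY <= 1470`, Week 204, AVISITN 18. This makes the grid contiguous from day 42 to day 2394.
2. Assign records entered on the case report form as the Post-Treatment Visit to a separate Post-Treatment analysis visit, including the post-treatment echocardiogram. Exclude them from the treatment-week windows and from the last-value rule. Using the nominal visit avoids dependence on a last-dose date that may be missing.
3. Keep End-of-Treatment and Premature Discontinuation records in the treatment-week windows, but flag those taken well after last dose. State the number of days that triggers the flag; without it some off-drug values would still pass unmarked.

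The cost is a few lines of SAP text and programming. No new data are needed.
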